### 3 OBJECTIVES AND ENDPOINTS

OBJECTIVES	ENDPOINTS	JUSTIFICATION FOR ENDPOINTS	PUTATIVE MECHANISMS OF ACTION
Primary			
To test the efficacy of the Intervention vs. Controls in increasing contact with, and utilization of, EBTs over a 7-month study period.	
 
-Any EBT contact over the 7-month study period.
 
-Total number of EBTs contacted – ranging 0 to 4 – over the 7-month study period
 
-EBT utilization index score over the 7-month study period
 
	Because effective cessation programs already exist, innovations are needed to drive smokers to engage with them. 40-80% of smokers are not ready to quit within 30 days, and efforts are needed to reach smokers with motivational interventions in their natural settings. Because we are proactively reaching patients, they may or may not be ready to quit smoking. Therefore, quit rates would be expected to be low if we were focusing on cessation, necessitating a very large sample to be able to compute power. The goal of the study is to test whether a clinic-based intervention that reduces provider burden and has minimal patient burden can drive patients to make contact with EBTs. Our prior research has shown that smokers who are not motivated to quit either lack knowledge about the EBTs, do not know how to access EBTs, and/or have myths about EBTs. The video-based intervention and subsequent 4-week text message program addresses these barriers, and provides motivational strategies to make contact with EBTs.	The VR video intervention including the subsequent 4-week text message program target social cognitive theory constructs (e.g., motivation, self-efficacy, outcome expectations) which are the hypothesized mechanisms that mediate the effect of the intervention on the primary study endpoints.
Secondary			
To test the efficacy of the Intervention vs. Controls in motivating smokers to use a combination of medication and counseling.	-Combination of at least one form of counseling EBTs (state quitline counseling, clinic-based counseling, text messaging) and at least one form of medication (nicotine replacement	Participants may utilize more than one EBT and will be encouraged to do so. Evidence shows that a combination of counseling and medication is more effective than either treatment alone.	

OBJECTIVES	ENDPOINTS	JUSTIFICATION FOR ENDPOINTS	PUTATIVE MECHANISMS OF ACTION
	therapy or tablet medication) over the 7-month study period.		

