attempts and increase their motivation to quit; 2) To test the efficacy of the Intervention vs. Controls on biochemically verified smoking abstinence. Hypothesis 3 states: Participants in the Intervention will achieve higher rates of point-prevalence abstinence at follow-up; 3) To assess the mechanisms through which intervention effects occur (mediators such as self-efficacy, motivation, and outcome expectations) and to identify subpopulations for whom intervention effects differ (moderators such as gender and motivation to quit). Hypothesis 4 states: The Intervention will directly affect the putative mediators of intervention effect, which will in turn affect EBT engagement (contact) and utilization. The role of moderators will be exploratory.

Participants will be randomized (1:1) at the dental clinic, after receiving the study brochure and before watching the videos during their teeth cleaning. Randomization will be implemented by employing a stratified block procedure with small, random size blocks and will be stratified by motivation to quit (ready to quit smoking in 30 days vs. not ready to quit within 30 days). To avoid randomization errors, randomization will be configured within REDCap, the secure web application used to build and manage the questionnaires and study forms which is programmed and managed by the BU Biostatistics and Epidemiology Data Analytics Center (BEDAC). A biostatistician will build the randomization program. The study RA will trigger randomization by pressing the feature on the REDCap eCRF form using an iPad. All dental providers will be masked to treatment condition because both the Intervention group and the Control group will be watching a video through the VR headset. Only the PI, project director, statistician, and study RA who is in the clinic will be unmasked to treatment condition.

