- EBTs for smoking cessation will be operationalized as: 1) utilization of any EBT over the 7-month study period; 2) total number of EBTs utilization during the 7-month study period (ranging 0 to 4); 3) EBT utilization index score (UIS; obtained by first computing a proportion of utilization score for each of the EBTs for each participant, and then adding up the individual proportion scores; see section 9.4.1 for details); 4) combination of at least one form of non-pharmacologic EBT and at least one form of pharmacologic EBT over the 7-month study period.
- Quit smoking attempts (assessed at Time 4 – 6). The number of quitting smoking attempts participants have made, since last contact, that have lasted 24 hours or more and that were not due to hospitalization or illness.
- Motivation to quit smoking (assessed at Time 4 – 6). Participants' motivation to quit smoking within 30 days (yes vs no).
- Smoking abstinence (assessed at Time 4 – 6). Seven-day point-prevalence abstinence (7-day ppa) assessed by self-report of no smoking, not even a puff, in the past 7 days and salivary cotinine level < 15 ng/mL.
- Mediators of treatment effects (assessed at Time 2 – 6). Theoretically driven constructs hypothesized to mediate any observed intervention effect (EBT utilization, quit smoking attempts, motivation to quit, or smoking abstinence) include the social cognitive theory constructs of motivation, self-efficacy, and outcome expectancies.
- Moderators or treatment effects (assessed at baseline). Moderating factors include sex, race or ethnicity, perceived stress and readiness to quit smoking.

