#### Secondary Endpoints:

We hypothesize that, compared to smokers who receive the Control intervention, smokers who receive the Intervention will:

- a) have more quit attempts during the 7-month study period (Aim 2 Hypothesis 2.1)
- b) have higher motivation to quit at 1-month post-appointment and 3- and 6-months follow-up (Aim 2 Hypothesis 2.2)
- c) have greater biochemically verified abstinence rates at 1-month post-appointment and 3 and 6 months follow-up (Aim 3 Hypothesis 3.1)

Alternatively, our null hypotheses are that there will be no difference between the two study groups on these secondary endpoints.

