Aim 2. Quit attempts and motivation to quit, and Aim 3. Biochemically verified abstinence. Dichotomous data on quit attempts, motivation to quit, and biochemically verified abstinence will be collected at one-month post-appointment (the end of the text message program), and at 3 and 6 months follow-up. Data on quit attempts will be based on the question "Since last contact, how many times have you stopped smoking for at least 24 hours because you were trying to quit smoking (not due to illness/hospitalization)?" Our main analyses for this outcome will examine the dichotomized outcome of 'any quit attempt', although we will collect data on the number of attempts and duration. Motivation to quit will be based on the question "Are you seriously thinking of quitting smoking in the next 30 days (yes or no)?" To determine point-prevalence abstinence, participants will be asked "In the last 7 days, have you smoked any cigarettes at all, even a puff?" For those responding 'no', biochemical verification will be implemented with salivary cotinine, with abstinence defined as cotinine values < 15 ng/mL. If participants indicate use of Nicotine Replacement Therapy or electronic nicotine delivery system use, these data will be recorded and reported separately from cotinine-validated abstinence. For these outcomes, the Intervention will be compared to the Control on data from 1-month post-appointment and at 3 and 6 month follow-up through mixed effect logistic regression models with random intercepts for longitudinal dichotomous data. These models will include indicator variables for intervention group, time, and interaction between intervention group and time (which will model and test whether changes in motivation to quit follows different patterns over time in the

Based on the NIH Behavioral and Social Intervention Clinical Trial Protocol Template v3.0 - 20180827

Intervention vs. Control group). Intervention effects will be described through odds ratios and 95% confidence intervals. In the case of significant intervention by time interaction, separate odds ratios will be given for intervention effects at each time point. We will control for age, gender, race/ethnicity, and variables identified through preliminary analyses as significantly differing between study groups.

---

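### The motivation-to-quit model in 9.4.3 omits the readiness stratum, which is in effect the baseline value of that outcome, and no planned analysis separates becoming ready from staying ready

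*Combined protocol and SAP*

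**What the plan says.** - **Hypothesis.** Section 4.1 (Hypothesis 2) predicts that the Intervention group will make more quit "attempts and increase their motivation to quit". Section 9.1 (Hypothesis 2.2) is a between-group statement: the Intervention group will "have higher motivation to quit at 1-month post-appointment and 3- and 6-months follow-up".
- **Outcome.** Section 8.1 defines it as "motivation to quit smoking within 30 days (yes vs no", and 9.4.3 gives the question: "Are you seriously thinking of quitting smoking in the next 30 days (yes or no".
- **Stratification.** Section 4.1, repeated in 6.3, has randomisation "stratified by motivation to quit (ready to quit smoking in 30 days vs. not ready to quit within 30 days".
- **Model.** Section 9.4.3 compares the arms on the 1-, 3- and 6-month data with "mixed effect logistic regression models with random intercepts for longitudinal dichotomous data". The terms are arm, time and arm by time.
- **Covariates.** "We will control for age, gender, race/ethnicity, and variables identified through preliminary analyses as significantly differing between study groups". Baseline readiness is not named.
- **Effect modification.** Sections 9.4.7 and 9.4.9 examine baseline readiness as a modifier of any EBT use only.
- **Expected mix.** Section 3 says that "40-80% of smokers are not ready to quit within 30 days". This is background, not an enrolment forecast.

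**The concern.** The outcome and the stratifier are the same 30-day yes/no construct. A participant who is ready at randomisation cannot score higher later; they can only stay at yes or fall to no. A participant who is not ready can only stay at no or move to yes. One odds ratio over everyone combines two different events, in proportions set by who was recruited.

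Two things follow. First, the baseline value of a binary outcome is usually among its strongest predictors, and here it is missing from the model. The rule that adds significantly differing variables is unlikely to bring it in, because stratified blocks are designed to balance it. Second, a reader could not tell a shift among unready smokers from maintenance among ready ones. The strata receive different videos and text tracks (4.3), so unequal effects are plausible. The arm-by-time term does not help: it compares follow-up visits with each other, not with baseline.

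**Working it through.** **1. The plan's own figure.** The formula is power = Φ[(|p1 − p0| − 1.96·SE0)/SE1], with SE0 from the pooled proportion and SE1 from the two separate ones. Section 9.2 gives 22.7% v 37.6% and 364 evaluable, so 182 per arm.
- Difference 0.149; SE0 = √(2 × 0.3015 × 0.6985/182) = 0.0481; SE1 = √((0.1755 + 0.2346)/182) = 0.0475.
- Power = Φ[(0.149 − 0.0943)/0.0475] = 0.875, against 0.87 stated.

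This is the primary endpoint. The documents give no rate, effect size or power for motivation, so all that follows is a scenario.

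**2. Inputs for motivation.** From the documents: 182 per arm, two-sided 0.05, and 20–60% ready at baseline (the complement of 40–80%). Assumed: one visit; 20% of not-ready controls become ready; 60–90% of ready controls stay ready; odds ratio 2.05 in the not-ready stratum, borrowed from the primary endpoint. That odds ratio turns 20% into 0.25 × 2.05/(1 + 0.25 × 2.05) = 33.9%.

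**3. Worked example: 40% ready, 75% of ready controls stay ready, odds ratio 2.05 in both strata.**
- Ready stratum: 75.0% v 3 × 2.05/(1 + 3 × 2.05) = 86.0%, difference 0.110. Not-ready stratum: 20.0% v 33.9%, difference 0.139.
- Pooled: control 0.4 × 0.75 + 0.6 × 0.20 = 42.0%; Intervention 0.4 × 0.860 + 0.6 × 0.339 = 54.7%; odds ratio 1.67. The drop from 2.05 is non-collapsibility of the odds ratio, not a weaker effect.
- Unadjusted: difference 0.1274, SE0 0.0524, SE1 0.0520. Power = Φ[(0.1274 − 0.1027)/0.0520] = 0.68.
- Stratified balance makes the true spread smaller. With within-stratum variances, SE1 = √(0.3536/182) = 0.0441, and unadjusted power is Φ[(0.1274 − 0.1027)/0.0441] = 0.71.
- Stratum-adjusted (Mantel-Haenszel approximation): same difference, SE0 = √(0.3618/182) = 0.0446, SE1 = 0.0441. Power = Φ[(0.1274 − 0.0874)/0.0441] = 0.82.

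A logistic simulation with 75%/25% control rates and odds ratio 2.05 in both strata agrees in direction. At 20/40/60% ready, power is 0.82/0.80/0.72 without the stratum and 0.87/0.86/0.82 with it, and the adjusted odds ratio returns to about 2.0–2.1.

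**4. Varying the effect in the ready stratum.** Ranges are over 20–60% ready and 60–90% staying ready. Unadjusted power uses the simple formula, without the balance allowance.

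| Odds ratio, ready stratum | Pooled odds ratio | Unadjusted power | Stratum-adjusted power | Not-ready stratum only |
|---|---|---|---|---|
| 1 (no effect) | 1.25–1.65 | 0.19–0.61 | 0.20–0.72 | 0.47–0.76 |
| 1.5 | 1.39–1.78 | 0.32–0.74 | 0.52–0.78 | 0.47–0.76 |
| 2.05 | 1.46–1.88 | 0.40–0.81 | 0.64–0.87 | 0.47–0.76 |

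Adjusting for the stratum raises power in every cell. The not-ready-only test beats the adjusted pooled test in the first row. It falls below it in every cell of the other two rows, by less than 0.01 in the closest.

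**The case against.** **The pooled odds ratio is diluted.** A reader might infer this as a fact, since ready participants cannot rise. The documents do not support it. Hypothesis 2.2 concerns status at follow-up, and a ready smoker who stays ready instead of lapsing counts properly towards it. Dilution needs a smaller effect in the ready stratum, and no stratum-specific rate or effect is given. Section 4.3 says the ready video also covers sustaining motivation for abstinence and that the texts target the mediators, of which motivation is one, so a nil effect there is not the natural assumption. If the ready-stratum effect were larger, the pooled odds ratio could even exceed the not-ready one: with 60%/30% control rates and odds ratio 3.0 in the ready stratum, it is 2.07–2.28.

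**The not-ready stratum should be the test of Hypothesis 2.** A reader might also infer this from the word *increase* in 4.1. It is a trade-off: the table shows a gain only when the ready-stratum effect is near nil.

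**The same item is used twice.** This goes too far. The construct and the 30-day horizon match, but the stratifier's question wording is not given.

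**Other handling.** The mediation analysis (9.4.9) uses change from baseline in motivation, but not by stratum and only in relation to EBT use. The planned random intercept gives subject-specific odds ratios and would recover part of the attenuation, so the single-visit figures overstate it. Section 9.4.1 promises a formal SAP before unblinding, which gives a place for the correction but does not supply it. These replies leave the omitted covariate and the missing stratum-specific report unanswered.

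**Conclusion.** The point holds as an omission in one secondary analysis. The readiness stratum is in effect the baseline value of the motivation outcome. The model does not name it, and nothing planned shows separately whether unready smokers became ready or ready smokers stayed so. In the worked example the omission costs 0.11 to 0.14 of power (0.71 or 0.68 against 0.82); in the simulated scenarios with equal effects it costs about 0.05 to 0.10. These sizes rest on assumed rates, a borrowed odds ratio and a single visit, and the planned three-visit model would change them somewhat. Dilution by unequal effects is possible but not established. Sections 4.1 and 9.1 also state different claims, and the planned model tests only the one in 9.1.

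**What to change.** In 9.4.3, or in the formal SAP before unblinding:

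1. Include the readiness stratum, as used at randomisation, as a covariate in the motivation model, whether or not the arms differ on it.
2. Keep the stratum-adjusted pooled comparison as the test of Hypothesis 2.2. Do not replace it with the not-ready stratum alone.
3. From a model with an arm-by-stratum term, always report the effect in each stratum, as becoming ready among the not-ready and staying ready among the ready. Label this a prespecified supporting analysis.
4. Reword Hypothesis 2 in 4.1 so that *increase* matches *higher* in 9.1.

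The cost is some wording, one covariate and one supporting model. The strata are already randomised and no new data are needed. The stratum-specific intervals will be wider than the pooled one, because each uses only part of the sample.

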## 4.2 SCIENTIFIC RATIONALE FOR STUDY DESIGN

Effective smoking cessation programs exist but are underutilized by smokers, particularly underserved smokers. Innovations are needed to increase engagement with these cessation programs. Incorporating smoking cessation into a dental clinic visit and targeting all smokers, regardless of motivation to quit, provides proactive reach to cigarette smokers who otherwise may not seek treatment for smoking. Our study measures EBTs contact and utilization as the study outcome rather than smoking cessation because not all participants may be ready to quit at the time of their dental appointment. Smokers who are not motivated to quit are also less likely to participate in intensive interventions. The video-based intervention serves as a low burden platform suitable for smokers who are unmotivated to quit because it is given during their teeth cleaning (e.g., doesn't require extra time).

Participants who are randomized to the control group will also watch a video of the same length as the intervention group (10 minutes), through the VR headset, while getting their teeth cleaned. The video was created in our previous NIH-funded study and uses guided imagery for relaxation. This video depicts a country setting and a voice-over helps viewers simulate perception of sounds, tastes, smells, movements, texture, temperature, and pressure. The country scene slowly changes (e.g., more flowers are grown, a bird flies by) to keep viewer's attention. Guided imagery has been extensively documented in the literature. We chose to use a 'guided relaxation video' because it is somewhat related to the teeth cleaning experience regarding easing dental anxiety and discomfort as opposed to showing a video on a neutral topic. We considered having the control group receive the same amount of text messages on a different topic but rejected this idea for several reasons: 1. Cost to build an equivalent "control" text message program with same features (customization, personalization, interactivity) to achieve equivalency with the intervention group, 2. Given that the control group will be receiving weekly assessments via texts, we did not feel the extra cost to have exact equivalency would be justified, and 3. Difficulty finding a control topic that would be engaging to unmotivated smokers, risking low program usage.

We decided to use two academically affiliated dental clinics because these clinics are more likely to encounter underserved patients. Underserved smokers are our target population because they are less likely to utilize EBTs. If the intervention is successful in this setting, it is likely to be successful in other clinics as well. Because the vast majority of the providers have outside clinical practices, this will help build an intervention that is generalizable.

We will encourage providers to implement best practice guidelines for smoking cessation. However, because it is not part of the research question, we will not be providing intensive trainings and

treatment fidelity checks on whether or not they are providing counseling. We will, however, ask patients if they received advice to quit from their provider.

### 4.3 JUSTIFICATION FOR INTERVENTION

Overview of the Intervention: The Intervention consists of: 1) smoking cessation video intervention via VR headset during teeth cleaning (one tailored for those who are ready to quit and one tailored for those who are not ready to quit; both are 10-minutes in length), 2) print materials about the EBTs, and 3) text message program for 4-weeks to motivate engagement with EBTs and reminder texts throughout the study period.

Content of the intervention video: Videos were created using a professional video company. Videos are a mix of narration, interviews, b-roll (video images related to the topic), graphics, and animations, and include a combination of personal anecdotes from smokers (some who are motivated to quit and some who are ambivalent) and guidance from health professionals. The tone of the videos are optimistic (it can be done), empathic (doing it is difficult) and collaborative (vs. prescriptive). We followed key principles for designing videos for low literacy populations and for facilitating attention, comprehension, recall and adherence. The “not motivated to quit” video focused on motivational interviewing (MI) principles (and also features [name], the founder of MI) empathizing that quitting is a difficult decision, reasons why people want to quit but delay quitting, how to resolve ambivalence about quitting, how smoking facilitates and hinders their values and goals, strategies for taking small steps towards quitting, dispelling myths about smoking cessation medications and emphasizing personal choice. The “motivated to quit” video provided greater detail on pharmacotherapy options, strategies to cope with triggers and withdrawal symptoms, benefits of quitting, creating new habits, avoiding slips, and sustaining motivation for abstinence. Both videos present information on EBT options, and how to seamlessly connect to them when ready to quit. Both videos also feature a dentist who narrates a 3D animation of the effects of smoking and quitting smoking on oral health.

Content of text message program: The text messages help to bridge the intervention video shown during the dental appointment and their ‘landing’ at an EBT. The text messages begin within one day of their dental appointment. Participants receive approximately two text messages per day for 4 weeks. The program is automated, interactive, and tailored and includes two different content tracks: one that is tailored for those who are motivated to quit within 30 days and one for those who are not motivated to quit within 30 days. Intervention text messages were explicitly written to target our mediators and we ensured that at least one message per week targets each of the three mediators, using an intervention mapping process that we have used in prior studies. Other message content includes debunking myths about nicotine replacement and tablet medication options, providing information about EBTs and what to expect, motivating utilization of EBTs, providing information about how to get reduced or no-cost pharmacological treatment for cessation, weekly assessments of hypothesized mediators, and connecting smokers to EBTs.

Rationale for content and platform: Our prior research has shown that smokers who are not motivated to quit either lack knowledge about the EBTs, do not know how to access EBTs, and/or have myths about EBTs. The video-based intervention and subsequent four-week text message program addresses these barriers, and provides motivational strategies to make contact with EBTs. Videos were not filmed in virtual reality because we believed that it would not have a differential effect on attitudes and

behavior (vs. a traditionally filmed video), that it would distract viewers from our core intervention messages, and that the head movement resulting from engaging with VR would interfere with clinical care. Watching a traditionally filmed video through a headset, however, enables continuous viewing of the video despite practitioner request for patients to turn their head, and it also enables a more immersive experience (increasing attention and possibly retention) vs. watching a projected video. Video-based interventions are effective at delivering health behavior interventions to low-literacy populations. We do not propose minimizing the role of the dental provider in smoking cessation, but rather provide a way to augment information without incurring extra time for both patients and providers. Research has shown that smoking cessation counseling is effective in dental settings, but requires time and training, and counseling practices are reduced after the research has ended. While providers may feel comfortable delivering smoking cessation to smokers who are ready to quit, the vast majority are reticent to counsel those who are not motivated to quit.

Rationale for Intervention content and frequency: The video intervention during the teeth cleaning is a clinically efficient use of time and low burden on patients and care providers. The 4-week text message curriculum program also requires low effort activity making it suitable for unmotivated smokers and low-income smokers. The program length is sufficient to provide information about EBTs, and motivate and facilitate patient's connection to EBT resources. A longer intervention may result in program disengagement. The end of treatment (4-week post-randomization), and the 3- and 6-months follow-up assessments allow the study team to assess the sustainability of EBT engagement. The vast majority of participants in both of our pilot studies indicated that the length of the video was 'just about right' (vs. too long or too short). Smokers who are unmotivated to quit are not likely to participate in intensive interventions that have a high amount of burden. Therefore, a video-based intervention that does not require additional time (it is shown during their teeth cleaning) and receipt of one month of text messages (a low effort activity) is a nice fit for unmotivated smokers. The length of the one-month text message program is appropriate for the goal: providing information about EBTs and motivating the smoker's connection to them. A longer program would be warranted if the text messages were focused on smoking cessation. We view the video as having a 'priming effect' to motivate smokers to make contact with the EBTs. Reminders of how to connect with EBTs will be sent via text message to the intervention group throughout the 7-month intervention period.

